#### **4.3 Selection and Timing of Dose for Each Subject**

Eligible subjects will receive treatment with nivolumab at a dose of 3 mg/kg, as a 60-minute IV infusion, on Day 1 of a treatment cycle every 2 weeks. Subjects must be treated within one day after study drug vial assignment. Dosing calculations should be based on the body weight assessed as per [Table 5.1-2](#). If the subject's weight on the day of dosing differs by > 10% from the weight used to calculate the dose, the dose must be recalculated. All doses should be rounded to the nearest milligram. There will be no dose escalations or reductions of nivolumab allowed. Subjects may be dosed no less than 12 days between doses and no more than 3 days after the scheduled dosing date. There are no premedications recommended for nivolumab on the first cycle. If an acute infusion reaction is noted, subjects should be managed according to [Section 4.3.6](#).

Treatment may be delayed for up to a maximum of 6 weeks from the previous dose (See [Sections 4.3.2](#) and [4.3.4](#)).

Tumor assessments by spiral CT/MRI for all subjects should continue as per protocol even if dosing is delayed.

Subjects will be monitored continuously for AEs while on study. Treatment modifications (eg, dose delay or discontinuation) will be based on specific laboratory and adverse event criteria.

### **4.3.1 Antiemetic Premedications**

Antiemetic premedications should not be routinely administered prior to dosing of drugs.

### **4.3.2 Dose Delay Criteria**

Dose delay criteria apply for all drug-related adverse events. Nivolumab must be delayed until treatment can resume (see [Section 4.3.4](#)).

Nivolumab administration should be delayed for the following:

- Any Grade  $\geq 2$  non-skin, drug-related adverse event, with the following exceptions:
  - Grade 2 drug-related fatigue or laboratory abnormalities do not require a treatment delay
- Any Grade 3 skin, drug-related adverse event
- Any Grade 3 drug-related laboratory abnormality, with the following exceptions for lymphopenia, leukopenia, AST, ALT, or total bilirubin:
  - Grade 3 lymphopenia or leukopenia does not require dose delay
  - If a subject has a baseline AST, ALT, or total bilirubin that is within normal limits, delay dosing for drug-related Grade  $\geq 2$  toxicity
  - If a subject has baseline AST, ALT, or total bilirubin within the Grade 1 toxicity range, delay dosing for drug-related Grade  $\geq 3$  toxicity
- Any adverse event, laboratory abnormality, or intercurrent illness which, in the judgment of the investigator, warrants delaying the dose of study medication.

#### **4.3.2.1 Management Algorithms for Immuno-Oncology Agents**

Immuno-oncology (I-O) agents are associated with adverse events that can differ in severity and duration than adverse events caused by other therapeutic classes. Nivolumab is considered an immuno-oncology agent in this protocol. Early recognition and management of adverse events associated with immuno-oncology agents may mitigate severe toxicity. Management algorithms have been developed to assist investigators in assessing and managing the following groups of adverse events:

Gastrointestinal

Renal

Pulmonary

Hepatic

Endocrinopathies

Skin

Neurological

For subjects expected to require more than 4 weeks of corticosteroids or other immunosuppressants to manage an adverse event, consider recommendations provided in the algorithms. These algorithms are found in the Nivolumab IB and in [Appendix 1](#) of this protocol. Discussions with the BMS Medical Monitor on how to apply these algorithms are strongly encouraged. The guidance provided in these algorithms should not replace the Investigator's medical judgment but should complement it.

#### **4.3.3 Doses Reductions and Escalations**

Doses reductions and escalations of nivolumab are not permitted.

#### **4.3.4 Criteria to Resume Nivolumab Dosing**

Subjects may resume treatment with nivolumab when the drug-related AE(s) resolve to Grade  $\leq$  1 or baseline value, with the following exceptions:

- Subjects may resume treatment in the presence of Grade 2 fatigue
- Subjects who have not experienced a Grade 3 drug-related skin AE may resume treatment in the presence of Grade 2 skin toxicity
- Subjects with baseline AST/ALT or total bilirubin in the Grade 1 toxicity range who require dose delays for reasons other than a 2-grade shift in AST/ALT or total bilirubin may resume treatment in the presence of Grade 2 AST/ALT OR total bilirubin
- Subjects with combined Grade 2 AST/ALT AND total bilirubin values meeting discontinuation parameters (Section 4.3.5) should have treatment permanently discontinued
- Drug-related pulmonary toxicity, diarrhea, or colitis must have resolved to baseline before treatment is resumed
- Drug-related endocrinopathies adequately controlled with only physiologic hormone replacement may resume treatment.

If the criterion to resume treatment is met, the subject should restart treatment at the next scheduled timepoint per protocol.

If treatment is delayed  $>$  6 weeks, the subject must be permanently discontinued from study therapy, except as specified in Section 4.3.5.

#### **4.3.5 Treatment Discontinuation Criteria**

Nivolumab treatment should be permanently discontinued for the following:

- Any Grade 2 drug-related uveitis or eye pain or blurred vision that does not respond to topical therapy and does not improve to Grade 1 severity within the re-treatment period OR requires systemic treatment
- Any Grade 3 non-skin, drug-related adverse event lasting  $>$  7 days, with the following exceptions for drug-related laboratory abnormalities, drug-related uveitis, pneumonitis, bronchospasm, hypersensitivity reactions, infusion reactions and endocrinopathies:
  - Grade 3 drug-related uveitis, pneumonitis, bronchospasm, hypersensitivity reaction, or infusion reaction of any duration requires discontinuation

- Grade 3 drug-related endocrinopathies adequately controlled with only physiologic hormone replacement do not require discontinuation
- Grade 3 drug-related laboratory abnormalities do not require treatment discontinuation except:
  - ◆ Grade 3 drug-related thrombocytopenia > 7 days or associated with bleeding requires discontinuation
  - ◆ Any drug-related liver function test (LFT) abnormality that meets the following criteria require discontinuation:
    - AST or ALT > 5 - 10 x ULN for > 2 weeks
    - AST or ALT > 10 x ULN
    - Total bilirubin > 5 x ULN
    - Concurrent AST or ALT > 3 x ULN and total bilirubin > 2 x ULN
- Any Grade 4 drug-related adverse event or laboratory abnormality, except for the following events which do not require discontinuation:
  - Grade 4 neutropenia ≤ 7 days
  - Grade 4 lymphopenia or leukopenia
  - Isolated Grade 4 electrolyte imbalances/abnormalities that are not associated with clinical sequelae and are corrected with supplementation/appropriate management within 72 hours of their onset
  - Grade 4 amylase or lipase abnormalities that are not associated with symptoms or clinical manifestations, or radiographic signs of pancreatitis. It is recommended to consult with the BMS Medical Monitor for Grade 4 amylase or lipase abnormalities
  - Grade 3 or 4 drug-related endocrinopathy AEs such as adrenal insufficiency, ACTH (Adrenocorticotropic Hormone) deficiency, hyper- or hypothyroidosis, or glucose intolerance, which resolve or are adequately controlled with physiologic hormone replacement (steroids, thyroid hormones) or glucose controlling agents, respectively, may not require discontinuation after discussion with and approval from the BMS Medical Monitor
- Any dosing interruption lasting > 6 weeks from the previous dose with the following exceptions:
  - Dosing interruptions to allow for prolonged steroid tapers to manage drug-related adverse events are allowed. Prior to re-initiating treatment in a subject with a dosing interruption lasting > 6 weeks, the BMS medical monitor must be consulted. Tumor assessments should continue as per protocol even if dosing is interrupted.
  - Dosing interruptions > 6 weeks that occur for non-drug-related reasons may be allowed if approved by the BMS medical monitor. Prior to re-initiating treatment in a subject with a dosing interruption lasting > 6 weeks, the BMS medical monitor must be consulted. Tumor assessments should continue as per protocol even if dosing is interrupted.
- Any adverse event, laboratory abnormality, or intercurrent illness which, in the judgment of the Investigator, presents a substantial clinical risk to the subject with continued nivolumab dosing.

- Disease progression (as determined by investigator assessment following the guidelines given in [Section 5.4](#)). Treatment beyond progression is allowed in certain instances as described in [Section 4.3.8](#).
- Subject who initiated the preparative regimen for allogeneic SCT or ASCT after the first dose of nivolumab treatment.

#### **4.3.6 Treatment of Nivolumab Related Infusion Reactions**

Since nivolumab contains only human immunoglobulin protein sequences, it is unlikely to be immunogenic and induce an infusion or hypersensitivity reaction. However, if such a reaction were to occur, it might manifest with fever, chills, rigors, headache, rash, pruritis, arthralgias, hypo- or hypertension, bronchospasm, or other symptoms. All Grade 3 or 4 infusion reactions should be reported within 24 hours to the BMS Medical Monitor and reported as an SAE if criteria are met. Infusion reactions should be graded according to National Cancer Institute (NCI) Common Terminology Criteria for Adverse Events (CTCAE) (Version 4.0) guidelines.

Treatment recommendations are provided below and may be modified based on local treatment standards and guidelines as appropriate:

**For Grade 1 symptoms:** (Mild reaction; infusion interruption not indicated; intervention not indicated)

Remain at bedside and monitor subject until recovery from symptoms. The following prophylactic premedications are recommended for future infusions: diphenhydramine 50 mg (or equivalent) and/or paracetamol 325 to 1000 mg (acetaminophen) at least 30 minutes before additional nivolumab administrations.

**For Grade 2 symptoms:** (Moderate reaction requires therapy or infusion interruption but responds promptly to symptomatic treatment [eg, antihistamines, non-steroidal anti-inflammatory drugs, narcotics, corticosteroids, bronchodilators, IV fluids]; prophylactic medications indicated for  $\leq 24$  hours).

Stop the nivolumab infusion, begin an IV infusion of normal saline, and treat the subject with diphenhydramine 50 mg IV (or equivalent) and/or paracetamol 325 to 1000 mg (acetaminophen); remain at bedside and monitor subject until resolution of symptoms. Corticosteroid or bronchodilator therapy may also be administered as appropriate. If the infusion is interrupted, restart the infusion at 50% of the original infusion rate when symptoms resolve; if no further complications ensue after 30 minutes, the rate may be increased to 100% of the original infusion rate. Monitor subject closely. If symptoms recur then no further nivolumab will be administered at that visit. Administer diphenhydramine 50 mg IV, and remain at bedside and monitor the subject until resolution of symptoms. The amount of study drug infused must be recorded on the electronic case report form (eCRF). The following prophylactic premedications are recommended for future infusions: diphenhydramine 50 mg (or equivalent) and/or paracetamol 325 to 1000 mg (acetaminophen) should be administered at least 30 minutes before

additional nivolumab administrations. If necessary, corticosteroids (recommended dose: up to 25 mg of IV hydrocortisone or equivalent) may be used.

**For Grade 3 or Grade 4 symptoms:** (Severe reaction, Grade 3: prolonged [ie, not rapidly responsive to symptomatic medication and/or brief interruption of infusion]; recurrence of symptoms following initial improvement; hospitalization indicated for other clinical sequelae [eg, renal impairment, pulmonary infiltrates]). Grade 4: (life-threatening; pressor or ventilatory support indicated).

Immediately discontinue infusion of nivolumab. Begin an IV infusion of normal saline, and treat the subject as follows. Recommend bronchodilators, epinephrine 0.2 to 1 mg of a 1:1,000 solution for subcutaneous administration or 0.1 to 0.25 mg of a 1:10,000 solution injected slowly for IV administration, and/or diphenhydramine 50 mg IV with methylprednisolone 100 mg IV (or equivalent), as needed. Subject should be monitored until the investigator is comfortable that the symptoms will not recur. Nivolumab will be permanently discontinued. Investigators should follow their institutional guidelines for the treatment of anaphylaxis. Remain at bedside and monitor subject until recovery from symptoms. In the case of late-occurring hypersensitivity symptoms (eg, appearance of a localized or generalized pruritis within 1 week after treatment), symptomatic treatment may be given (eg, oral antihistamine, or corticosteroids).

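### Protocol 4.3.6: the Grade 2 instruction for symptoms that return after restart overlaps with the printed Grade 3 definition, and no sentence tells the site to regrade

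*Protocol*

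**What the plan says.** All of this is in the Protocol.

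- **4.3.6, Grade 2 (labelled moderate).** Stop the infusion and treat. If it was interrupted, "restart the infusion at 50% of the original infusion rate when symptoms resolve". On recurrence, "If symptoms recur then no further nivolumab will be administered at that visit". The paragraph then continues: "The following prophylactic premedications are recommended for future infusions".
- **4.3.6, Grade 3 or 4 (Grade 3 labelled severe).** The features listed for Grade 3 include "recurrence of symptoms following initial improvement". The action is "Nivolumab will be permanently discontinued".
- **4.3.5.** "Grade 3 drug-related uveitis, pneumonitis, bronchospasm, hypersensitivity reaction, or infusion reaction of any duration requires discontinuation".
- **4.3.6, opening paragraphs.** Reactions are graded by CTCAE version 4.0. Grade 3 or 4 reactions go to the Medical Monitor within 24 hours. The treatment advice that follows may be adapted to local standards.
- **4.3.4.** "Subjects may resume treatment with nivolumab when the drug-related AE(s) resolve to Grade" 1 or to baseline, with listed exceptions. Then: "If the criterion to resume treatment is met, the subject should restart treatment at the next scheduled timepoint per protocol".

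**The concern.** Symptoms that resolved and then came back after restart are addressed by the Grade 2 recurrence sentence. They also fit the recurrence item in the Grade 3 definition. The grade the site settles on decides what follows. Kept at Grade 2 and resolved, the event leads back to dosing under 4.3.4. Graded 3, it ends treatment and triggers the 24-hour notice.

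At stake are re-exposure of a subject whom the protocol's own definition would take off drug, a missed notice to the Medical Monitor, and different handling between sites. The population gives some reason to care: exclusion criterion 4b (Section 3.3.2) admits subjects with an earlier Grade 3 or 4 reaction to a first rituximab dose, provided later rituximab caused no such recurrence.

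**Working it through.** No power, alpha or event figure is involved, so the check is a comparison of texts.

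**Step 1. Do the two descriptions overlap?** The Grade 2 sentence applies after symptoms have resolved and the infusion has been restarted. The Grade 3 item requires recurrence after improvement. Resolution is a complete form of improvement, so a recurrence after resolution meets the Grade 3 wording. In that definition recurrence is a separate item, set off by semicolons from prolonged reactions and from hospitalization, and carries no further condition of its own.

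**Step 2. Do the consequences differ?**

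| | Kept at Grade 2 | Graded 3 |
|---|---|---|
| That visit | No more drug | No more drug |
| Later doses | Possible, with premedication, once 4.3.4 is met | None (4.3.5, 4.3.6) |
| Medical Monitor notice within 24 hours | Not required by grade | Required |

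The immediate action is the same. Later dosing and the notice differ.

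**Step 3. Does any sentence settle the grade?** Section 4.3.6 names CTCAE as the standard. Neither the Grade 2 paragraph nor the Grade 3 paragraph tells the site to regrade when a restart fails, and the premedication sentence is not limited to subjects without recurrence.

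**Step 4. How soon could a further dose come?** Section 4.3 sets at least 12 days between doses and at most 3 days after the scheduled date. With a 14-day cycle, the latest dose without a delay is at 14 + 3 = 17 days. If the event is kept at Grade 2 and meets the resume criterion, the next dose could come 12 to 17 days after the interrupted one. Delay is allowed up to 6 weeks from the previous dose, so this is the undelayed window and not a prediction.

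**Step 5. Effect on the primary analysis.** The ORR denominator is all treated subjects (8.3.1), and a subject with an infusion reaction has already been treated. The change in denominator is 0, and the criterion of 27 responders out of 90 (8.4.2.1) stands.

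**The case against.** The best case against is that the section already separates the two situations by severity. Grade 2 is headed moderate and described as responding promptly; Grade 3 is headed severe. On that reading the Grade 2 sentence covers symptoms that return at moderate or lower intensity, and only a severe relapsing reaction is Grade 3. The Grade 2 sentence is also the only one that mentions restart, so it may be taken as the specific rule. Limiting the instruction to that visit then makes sense as the immediate order before grading is settled, and as the continuing rule for reactions that stay at Grade 2. The paragraphs are recommendations open to local adaptation, and once a grade is fixed, 4.3.5 gives one answer.

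Much of this stands. A reader might infer that the protocol gives two binding and contradictory orders for one event. The documents do not support that: the severity labels and the grading standard allow a coherent reading.

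What the objection does not do is make that reading the only one. Recurrence is listed as a Grade 3 feature in its own right, and the text does not say that a moderate recurrence stays at Grade 2. The freedom to adapt treatment advice does not reach the separate stop rule in 4.3.5.

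**Conclusion.** The overlap is real and the severity is minor. A site following the Grade 2 paragraph as printed could dose again a subject who meets the printed Grade 3 wording, and could omit the 24-hour notice.

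The consequence is bounded. Drug stops at once either way. Section 4.3.5 requires discontinuation where the investigator judges that further dosing carries substantial risk, and Section 6.1.1 requires any serious event to be reported within 24 hours whatever its grade. A recurrence that is neither serious nor judged a substantial risk is caught by neither backstop.

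Two further inferences would go too far. One is a count of re-exposed subjects: the documents give no infusion-reaction rate, so none can be derived. The other is harm to the efficacy result: the ORR method, denominator and success criterion are unchanged.

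The conclusion rests on the definition as printed in the protocol; the full CTCAE text is not among the documents.

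**What to change.** In the Grade 2 paragraph of 4.3.6, directly after the sentence withholding drug on recurrence, add: *Regrade the reaction; a recurrence that meets the Grade 3 definition below is managed under the Grade 3 paragraph (permanent discontinuation, 24-hour notice to the Medical Monitor).* Limit the sentence on premedication for later doses to reactions that remain Grade 2 after regrading.

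This keeps grading with the definition already printed and adds no free-standing rule that every recurrence is Grade 3. If the sponsor intends a moderate recurrence after restart to stay at Grade 2, the definition should say so.

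The cost is one sentence, one limiting clause and a memo to sites, with no extra data or subjects. The downside is that an occasional subject with recurrence loses further dosing; the documents give no rate from which to say how often.

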#### **4.3.7 Guidelines for Assessment and Management of Tumor Lysis Syndrome**

The possibility of tumor lysis syndrome cannot be ruled out for the subjects with lymphoma. Therefore, adequate management such as hydration and/or the use of allopurinol is recommended in the subjects who have risk factor of potential tumor lysis syndrome, for example the subjects with high tumor burden, reflected by high serum LDH levels, or bulky disease, or those with preexisting renal failure.

#### **4.3.8 Treatment Beyond Disease Progression**

##### **4.3.8.1 Circumstances in which Post-progression Treatment is Permitted**

Subjects meeting progression defined by relapsed disease (after CR) or progressive disease (after PR, SD) per 2007 IWG criteria may continue receiving study medication beyond investigator-assessed progression as long as they meet the following criteria:

- Continue to meet all other study protocol eligibility criteria
- Investigator-assessed clinical benefit, and do not have rapid disease progression
- Stable performance status
- Treatment beyond progression will not delay an imminent intervention to prevent serious complications of disease progression
- Patients will be re-consented with an informed consent document describing any reasonably foreseeable risks or discomfort and other alternative treatment options
- Tolerance of study drug

The decision to continue treatment beyond investigator-assessed progression should be discussed with the BMS Medical Monitor and documented in the study records. The assessment of clinical benefit should take into account whether the subject is clinically deteriorating and unlikely to receive further benefit from continued treatment.

#### **4.3.8.2 Assessment schedule for the subjects with post-progression treatment**

The subject should continue to receive monitoring according to the On-Treatment Assessments on [Table 5.1-2](#) except for FDG-PET scans. Radiographic assessment by CT (preferred) or MRI described in the [section 5.4.1](#) and [Table 5.4.1-1](#) are required when subjects continue post-progression treatment. FDG-PET scans are not mandated after investigator-assessed progression.

#### **4.3.8.3 Discontinuation due to Further Progression**

Subjects should discontinue study therapy upon evidence of further progression, defined as an additional 10% or greater increase in tumor burden volume from time of initial progression (including all target lesions and new measurable lesions).

- Further progression is evaluated by a subsequent CT or MRI which is performed at least 8 weeks from previous CT or MRI.
- The tumor burden volume from time of initial progression should be used as the reference baseline for comparison with the post-progression assessment.
- New lesions are considered measurable at the time of initial progression if the long axis is more than 15 mm regardless of the short axis. If a lymph node has a long axis of 11 to 15 mm, it should only be considered measurable if its short axis is more than 10 mm.
- Any new lesion considered non-measurable at the time of or after initial progression may become measurable and therefore included in the tumor burden determination.

#### **4.3.8.4 Radiographic Assessment for Subjects who Discontinue Study Drug during Post-progression Treatment**

For subjects that discontinue post-progression treatment, no additional radiographic assessments will be required. Upon treatment discontinuation, these subjects will continue in the follow-up phase of the study (see [Section 5.1](#)). Subjects who proceed to allogeneic SCT or ASCT will be followed as described in [Section 5.4](#).

